REDCap (Research Electronic Data Capture). All case report forms for the trial will be captured using a secure web-based data capture system REDCap. REDCap under the direction of the UCSD ACTRI Biomedical Informatics division offers and manages REDCap. The ACTRI Biomedical Informatics team will maintain and provide full administration and support for REDCap. Data captured electronically in the delivery room will be uploaded to REDCap for future analysis for all sites. The REDCap application supports many data collection and analysis projects. Data collection projects rely on a thorough study-specific data dictionary defined in an iterative self-documenting process by all members of the research team with planning and analytic assistance from biostatisticians. The iterative development and testing process results in a well-planned data collection strategy for individual studies. The REDCap system provides secure, web-based applications that are flexible enough to be used for a variety of types of research, provide an intuitive interface for users to enter data and have real time validation rules (with automated data type and range checks) at the time of entry. The system has been deployed using a highly secure, HIPAA-compliant network design and is housed in a physically secure data center. Back up of data is performed nightly and archived off-site for two years for Disaster Recovery purposes. Principal investigators may opt to archive the data for up to seven (7) years offsite to AWS Glacier.

Data that will be accessed, used and collected will be identifiable on research-related forms by a study number. We will take the following precautions to maintain the confidentiality of identifiable subject information. We will also keep subject's identity separate from their data on a Master log and coded.

1. Paper-based records will be kept in a secure location and accessible only to persons involved in the study
2. Computer-based files will be available only to persons involved in the study through the use of access privileges and passwords.
3. Prior to accessing any PHI, personnel will be required to sign statements agreeing to protect the security and confidentiality of identifiable health information
4. Whenever feasible, identifiers will be removed from study-related information

Data Collection

Under waiver of individual HIPAA, we will collect the following minimal data set from all eligible subjects (parents that opt out will not be included):

Screening ID, Month/Year of birth, gestational age, SGA, time of cord clamping, Breathing or crying prior to cord clamping, birth assessment of tone, number of times cord milked, location of infant when milked (i.e. mothers abdomen, below level of introitus) birth weight, gender, APGARS at 1 and 5 minutes, resuscitation procedures (CPAP, PPV, intubation, chest

compressions, epinephrine, max FiO₂), NIRS data, disposition (NICU admission, or stable and staying with parent), pregnancy and delivery risk factors (diabetes, suspected or confirmed Triple I, hypertension, rupture of membranes).

After Informed Consent we will collect the following full data set:

Maternal data from infant's chart: Age, Race/Ethnicity, Level of Education, Mode of Delivery, Anesthesia (general, Spinal Epidural), Medications, Placental Weight. All maternal data will be collected from the infant's chart; the mother's chart will not be accessed for study purposes.

Infant data: Includes all data collected under waiver, plus Race/Ethnicity, Multiple gestation, length (cm), head circumference (cm), Hemoglobin between 12-48 hrs, Venous and/or arterial cord pH (if available), cardiac US, Peak total serum bilirubin (mg/dL) or Transcutaneous Bilirubin level, Polycythemia in the first week of life (Hct >65%), Duration of phototherapy days, Use of cardiac inotropes (dopamine, dobutamine, epinephrine), Early onset sepsis (positive blood or CSF culture at < 72 HOL), Duration of intubated and mechanical ventilation (days), Need for blood transfusion (DOL of 1st transfusion and total number), Length of hospitalization (total days), ASQ3, MCHAT, MRI white matter injury, HIE: mild, moderate, severe (initial screen completed at 1-6 hours of life), HIE: mild, moderate, severe (highest stage before discharge), Therapeutic Hypothermia, Placental pathology, PPHN.

Notification of Parents prior to enrollment: Both mother and baby will be subjects in this study. We are informing parents in three ways. First, all obstetric practices that refer babies to the study hospitals will have information such as brochures in their offices, at prenatal childbirth education classes and the obstetrician will discuss hospital's participation in the study with their patients. Second, there will be signs (to be developed from handout) about the study at prenatal sites and physician offices. Both will have information for parents about contact information of the researchers. Finally, there will be information about the study on the Sharp website with answers to frequently asked questions. High visibility posters of the study and information brochures will be posted in the hospitals for limited to no prenatal care situations and for those that may not have access to internet resources. All documents created for parent notification will be submitted for IRB approval before use.

Protocol Deviations

The following deviations will be entered on the Deviation Report Form in REDCap as they are identified:

- Cord clamping ≥ 60 seconds will be considered a protocol violation and analyzed due to the confounding effects of delayed cord clamping.
- Patient did not receive correct treatment arm.

Serious Adverse Events (SAE)

All SAE's of death, polycythemia/jaundice requiring exchange transfusion, pulmonary hemorrhage or severe IVH (grade 3 or 4) on HUS or MRI will be reported within 3 days of discovery of event, to UCSD DCoC via REDCap. The DCoC will forward all SAE reports to the DSMB and PI.

Unanticipated Event or Problems

The investigator will be responsible for reporting an unanticipated adverse event in REDCap, if it meets all of the criteria listed below:

1. It is an unexpected event (nature, severity or frequency) and not addressed within the study protocol or informed consent document
2. It is related or possibly related to the research as determined by the PI – there is a reasonable possibility that the event may have been caused by the procedures involved in the research
3. And suggests that the research places the subject or others at a greater risk of harm than was previously known or recognized (including physical, psychological, economic, or social harm)

If the unanticipated event is determined serious by the PI, it must be reported to the DCoC within three (3) days in REDCap; within 14 days for a Non-serious unanticipated event. The DCoC will report this to the DSMB who will determine if the adverse event changes the known risk to study subjects. If the information changes the known risk to subjects, the DSMB's report regarding the change in risk will be released to all participating investigators. The DSMB may request changes to the DSMP.

Data Safety Monitoring Board (DSMB)

A DSMB has been established to:

- 1) Protect all study patients
- 2) Safeguard the interests of all study patients
- 3) Monitor the overall conduct of the trial
- 4) Advise the investigators to protect the integrity of the trial, and
- 5) Supervise the conduct and analysis of all interim analyses.

The DSMB will receive regular reports from the trial on any injuries or adverse events, any developments that jeopardize the continued success of the trial, and data by which to accomplish the evaluation of pre-determined early stopping rules. All Serious Adverse Events (**SAEs**) will be reported within 3 days of discovery to the Data Coordinating Center (**DCoC**) and forwarded to the DSMB; reports of adverse events and recruitment will be sent monthly; demographics will be included with the interim and final safety and efficacy analyses. The DSMB will conduct interim analyses and project statisticians, independently from the trial leadership and staff. The role of the trial investigators is to notify the IRB of any issues that are relative to patient safety or to early stopping of the study. The study will be closely monitored for issues of data quality, study conduct, and adverse events. These analyses will be presented to the DSMB.

Trial Timeframe

Trial stages	Timeframe
Protocol development	April- June 2018
Protocol finalized	July 2018
Site determination	June 2018, Investigator Meeting
Sites submit IRB application	July-August 2018
Finalize contracts and payment methods	September-October 2018
Site Randomization and education	October – December 2018
Recruitment phase	January 2019- March 2021
Assessment phase	Primary outcome June 2021
Analysis	2021 for primary outcome, 2023 for neurodevelopmental outcomes
Publication	2021 on primary outcome, 2023 for neurodevelopmental follow-up

Publication Plan

The trial will be registered on ClinicalTrials.gov prior to the randomization of the first site. The Publications and Presentations (P&P) policies and procedures for this trial can be modeled after those that have been used successfully in other studies. These will be developed, implemented, and enforced by a P&P Committee, chaired by a to-be-named individual for the trial, with representation of study members from the trial. The P&P policies and procedures will be developed as part of the Manual of Operations and communicated to participating sites as part of the site initiation activities. All investigators will be encouraged to participate in opportunities for presentation and publications; resources within the DCoC will be available to facilitate this. These policies will provide for optimizing the use of the valuable data collected by the study and provide an additional non-financial incentive for participating investigators.

Statements of compliance

The clinical investigation will be conducted in accordance with the ethical principles that have their origin in the Declaration of Helsinki. The clinical investigation will comply with the relevant national regulations of each participating medical center, and will not begin until required approvals from ethical committees have been obtained. Additional requirements imposed by the ethical committees will be followed. The clinical investigation will be conducted in accordance with this protocol.

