Aims/Hypotheses	
Specific Aim 1 - (PRIMARY): Compare the incidence of admission to the NICU in 35⁰-41⁶ week GA non-vigorous newborns receiving Umbilical Cord Milking (UCM) to those receiving Early Cord Clamping (ECC).
 
H1: Compared to ECC subjects, UCM subjects will have a decreased incidence of NICU admission (based on predefined criteria).
 
Specific Aim 2 (SECONDARY): Compare the safety and efficacy profiles in 35⁰-41⁶ week GA non-vigorous newborns receiving UCM to those receiving ECC. Compared to ECC subjects, UCM infants will have:
 
H2: Higher cerebral oxygen saturations in the first 10 minutes of life (sub-study at two (2) sites, n=20).
 
H3: Receive a greater placental transfusion as estimated by hemoglobin levels by 48 hours of life and better blood pressure; will not have increased rates of hyperbilirubinemia compared to ECC subjects; will have decreased resuscitation interventions, level of HIE, use of therapeutic hypothermia, use of volume expanders, and length of hospitalization.
 
H4: Will have improved developmental outcome scores on the Ages & Stages Questionnaire, Third Edition (ASQ-3); UCM subjects will have a lower rate of medium to high risk scores on the MCHAT at 2 years of age.
 
H5: Better cardiac function as measured by echocardiography at 12 hours of life (sub-study at two (2) sites, n=200).

Design and Sample Size	This prospective multi-national cluster randomized crossover (CRXO) trial randomizes by hospital wherein each institution is randomized over time to each arm of the study n=1200 infants – 600 UCM/600 ECC
Inclusion Criteria	
 Non-vigorous newborns born between 35⁰-41⁶ weeks gestation
Exclusion Criteria	
 Known major congenital or chromosomal anomalies of newborn Known cardiac defects other than small ASD, VSD and PDA Complete placental abruption/cutting through the placenta at time of delivery Mono-chorionic multiples Cord anomaly (i.e. avulsion or true knot) Presence of non-reducible nuchal cord Perinatal providers unaware of the protocol Incomplete delivery data Infants born in extremis, for whom additional treatment will not be offered

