Our pre-specified inclusion criteria will minimize selection bias since infant appearance at birth, rather than actual cord management, determines which infants are included. Allocation bias will be prevented since all non-vigorous infants will receive the same treatment during the prescribed epoch. It is impossible to blind obstetrical providers or parents to the assigned treatment arm. To avoid clinical team bias we will request documentation of the specific intervention (UCM or ECC) not be included in the infant's medical record. Since cord management is not routinely provided in the medical record we have specifically avoided any inclusion of the management to avoid downstream bias once the study has begun. In order to prevent admission bias in either of the prescribed epochs, we have outlined pre-specified criteria that will constitute a NICU admission for purposes of this study, see appendix 2.

Specific Aim 2 (SECONDARY) Compare the safety and efficacy profiles of non-vigorous newborns 35-41+6 weeks GA delivered receiving UCM vs. ECC during their birth hospitalization and at 24 months corrected age.

H2: Compared to ECC subjects, UCM subjects will have higher cerebral oxygen saturations at 10 minutes of life (sub-study at three (3) sites, n=20).

Rationale: Caregivers and researchers raised theoretical concerns that the UCM technique may deliver blood rapidly toward a non-vigorous newborn predisposing them to higher rates of brain injury or dislodging cellular debris into the brain. However, of the 13 studies on term infants comparing UCM to ECC, none have reported adverse outcomes. All demonstrated improvements similar to DCC with increased red cell mass (measured by hematocrit or hemoglobin) improved blood pressure, increased pulmonary blood flow and improved ferritin at 6 weeks to 6 months of age with UCM. Nevertheless, careful assessment of safety is essential. Immediate physiological measurements on a subset (n=20) of infants of the three sub-study sites where the use of NIRS is standard of care, University of Alberta, SMBHWN and SGH to establish the safety and efficacy of UCM. This aim will further test our hypotheses that infants in the UCM group will have improved early cardiac and cerebral hemodynamics within the first 10 minutes.

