At the three sub-study sites, the use of NIRS is standard of care and therefore will be collected along with other data as part of the minimal data set. As part of the NIRS sub-study, sites will collect physiological and resuscitation data from birth (mean airway pressure, fractional oxygen) in addition to cerebral oxygenation. Once the newborn is delivered, receives the intervention (UCM or ECC), and is stabilized during resuscitation, a NIRS sensor (Fore-Sight, CAS Medical, Branford, CT) will be placed on the right forehead within 10 minutes of life. While arterial saturation and heart rate data will be available to the clinical team, data from NIRS will be blinded. Data on all study infants will be recorded for the first 10 minutes in the delivery room at the three sites. Heart rate, oxygen saturations, and cerebral oxygenation will be downloaded as per site's practice for neonatal resuscitation. If an enrolled infant has recovered and is stable enough for maternal bonding, NIRS may be discontinued prior to 10 minutes of life and will not be a protocol deviation.

H3: UCM subjects will receive a greater placental transfusion as estimated by hemoglobin levels by 48 hours of life and better blood pressure; UCM subjects will not have increased rates of hyperbilirubinemia compared to ECC subjects; UCM subjects will have decreased incidence and severity of HIE, decreased resuscitation interventions, decreased use of therapeutic hypothermia and use of volume expanders, and a shorter length of hospitalization.

Rationale: These variables are chosen to assess the efficacy (hemoglobin) as well as safety (bilirubin) of both cord interventions. Data will be collected from the subject's chart.

H4: UCM subjects will have improved developmental scores on the Ages & Stages Questionnaire at 2 years of age and UCM subjects will have a lower rate of medium to high-risk scores on the MCHAT at 2 years of age.

Neurodevelopmental Follow-up Strategy

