Appendix 1 Data Collected**DATA COLLECTED ABOUT INFANTS
AND MOTHERS****Maternal data from infant's chart:**

1. Age
2. Race/Ethnicity
3. Diabetes (gestational, Type 1 or 2) (yes/no)
4. Suspected or confirmed Triple I, chorioamnionitis (yes/no)
5. Hypertension (yes/no)
6. Rupture of Membranes (hours)
7. Mode of Delivery
8. Type of Anesthesia
9. Maternal medications (i.e. magnesium, fentanyl)
10. Placental Weight
11. Level of education
12. COVID-19 confirmed positive

**Data collected from all eligible infants
under waiver:**

13. Screening ID
14. Month/Year of birth
15. Birth assessment of tone
16. ECC or # times Milked
17. Timing of cord clamping
18. Breathing/Crying before cord clamped
19. 1 and 5 min Apgar
20. Resuscitation interventions (cpap, ppv, intubation, compressions, epinephrine, max Fio2)
21. NIRS, HR, SpO2 in del room
22. Gestational Age
23. Birth Weight
24. Gender
25. Disposition(NICU, Death or Dyad care)
26. Infant/delivery risk factors
27. NICU admission Dx
28. Reason Peds called to delivery
29. Multiple Gestation
30. COVID-19 confirmed positive

Infant data collected after consent:

31. Length, FOC (cm)

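### The NIRS hypothesis (H2) is set at 20 infants although NIRS is to be recorded on every study infant at the NIRS hospitals, and nothing says whether 20 is a cap or how it is spread over hospital and epoch

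*Combined protocol and SAP*

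**What the plan says.** **Size.** Section IV, Specific Aim 2, gives H2 as "sub-study at three (3) sites, n=20", and its rationale describes "Immediate physiological measurements on a subset (n=20) of infants of the three sub-study sites where the use of NIRS is standard of care". The text on NIRS that follows repeats n=20. The Protocol Summary has "sub-study at two (2) sites, n=20", so the number of sites also differs.

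**Who is recorded.** Under Protocol for NIRS Sub-Study, at the three sites "the use of NIRS is standard of care and therefore will be collected along with other data as part of the minimal data set", and "Data on all study infants will be recorded for the first 10 minutes in the delivery room at the three sites". Section IX, Data Collection, says of that set that "we will collect the following minimal data set from all eligible subjects", apart from opt-outs, and names NIRS data in the list. Appendix 1, item 21, lists "NIRS, HR, SpO2 in del room" among the data taken from all eligible infants under the waiver.

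**Selection and analysis.** No rule says which infants make up the 20, or how they divide by arm, hospital or epoch. The only analysis statement, at the end of the statistics section, is that the sub-studies are registered, reported and analysed separately.

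**Timing.** Under Timeline (Section III), a hospital stays in one arm until it reaches half its target or one year, whichever comes first. Appendix 4 shows one of the three NIRS hospitals being added in version 1.8, dated 12 November 2020. The Trial Timeframe table has recruitment running from January 2019 to March 2021.

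**The concern.** The analysis set for H2 is not defined. One part of the plan points to 20 infants and another to every study infant at the NIRS hospitals.

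Two things are at stake. The first is precision. The rationale says the measurements are meant to establish both the safety and the efficacy of milking, and about 10 infants per arm cannot carry that claim. The second is the comparison itself. The protocol relies on each hospital's crossover to account for site differences (Section IV, Expectations, Limitations & Alternatives). That protection reaches H2 only if its infants come from both epochs at each hospital. Twenty infants taken without regard to epoch could leave a hospital in one arm only, so that differences between hospitals mix with the treatment difference. The hospital added in November 2020 could be in that position even if all its later traces are used.

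**Working it through.** **1. The plan's own figure.** The documents give no effect size, SD, power or allowance for loss for n=20, so it cannot be reproduced. What it delivers can be calculated in SD units.

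**2. Precision.** Inputs: two-sided alpha 0.05 (statistics section); equal arms, independent infants and no loss (assumed).

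- 95% CI half-width for a difference in means = t(0.975, 2n−2) × √(2/n). For n=10 per arm: 2.101 × 0.447 = 0.94 SD.
- Detectable difference at 80% power, normal approximation: (1.960 + 0.842) × √(2/10) = 1.25 SD. The noncentral t gives 1.32 SD.
- Power at 10 per arm: 18% for a 0.5 SD difference and 56% for 1.0 SD.

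**3. What more traces would give.** The number of usable 10-minute values is not stated, so this is a range and not a forecast. Clustering is ignored.

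| Per arm | Basis (assumption) | CI half-width, SD | Detectable at 80%, SD |
|---|---|---|---|
| 10 | stated n=20, equal split | 0.94 | 1.32 |
| 60 | arbitrary: one third of 180 | 0.36 | 0.52 |
| 100 | echo target of 200 at two of the three hospitals | 0.28 | 0.40 |
| 180 | equal site sizes, every infant usable: 1200 × 3/10 ÷ 2 | 0.21 | 0.30 |

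**4. Selection.** Two hypothetical rules show why a rule is needed.

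- *First 20 consecutive infants.* If 200 to 360 infants yielded traces over 24 months, that is 8.3 to 15 a month, and 20 would be reached in 20/8.3 = 2.4 to 20/15 = 1.3 months. That lies inside a 12-month epoch, so each hospital would supply one arm only.
- *Random 20 of 360* (three equal hospitals, two equal epochs). In simulation, the chance that at least one hospital lacks an arm was about 14%.

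**5. The late site.** From 12 November 2020 to March 2021 is about four months, against an epoch of up to twelve. The documents do not give that hospital's start or crossover date. It may contribute one arm only, unless earlier standard-of-care traces are used.

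**The case against.** A reader might infer that the trial throws away most of its NIRS data. The documents do not say so. No passage states that traces beyond 20 are dropped, all NIRS data stay in the minimal data set, and 20 could be a minimum or a feasibility target.

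A reader might also infer that some 360 traces are waiting to be analysed. That is not supported either. The sample size section gives 1200 across ten sites without saying that the sites are equal. The sensor goes on only once the infant is stabilised, at any time within the first 10 minutes, and may come off early without a deviation, so many infants may have no 10-minute value. Appendix 4 shows the sub-study cut to 20 in version 1.7 and a hospital added in version 1.8 with 20 unchanged. That suggests usable traces were scarce, and it makes a sub-study filled within weeks less likely.

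Third, confounding of arm with hospital is a possibility and not a finding. Every hospital crosses over, the first-20 rule is hypothetical, and the late site's position depends on dates not given. H2 is also a mechanistic secondary question, separately registered, so further rules may exist in records not available here.

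All of this limits the size of the point. It does not say what 20 means or how the infants are chosen. If traces are scarce, the statement that all study infants are recorded needs correcting, and balance over site and epoch matters more.

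**Conclusion.** The point holds as an undefined analysis set with an avoidable loss of precision and of protection against site differences. As written, H2 could rest on about 10 infants per arm, with a half-width of 0.94 SD and a detectable difference of 1.32 SD. These figures assume an equal split, independent infants and no loss. That cannot support a claim about safety and efficacy. The gain from using every trace depends on an unstated count; the range of 0.36 to 0.21 SD for 60 to 180 per arm is illustrative only. Using all available traces does no harm however many there are. The primary analysis and the main sample size are not affected. The change is worth making, but it concerns a secondary sub-study.

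**What to change.** - Define the H2 analysis set as every study infant at the NIRS sites with a usable trace, from both epochs, analysed by assigned arm with site and period terms as in the primary analysis.
- Restate 20 as a minimum. If it is a true cap, take equal consecutive numbers from each site in each epoch.
- Describe separately any site with traces from one epoch only, and say whether traces recorded before a hospital joined the sub-study are used.
- Report by arm how many infants have and do not have a 10-minute value.
- Reconcile two sites (Protocol Summary) with three (Section IV).
- Soften the statement in the H2 rationale that these measurements will establish safety and efficacy.

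The cost is revised wording and the processing of traces that the sites already record. No infant undergoes an added procedure.
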